Overall, approximately 1687 subjects have received midostaurin including ~650 patients with AML / MDS. In AML patients, doses of up to 600 mg per day have been given, but the 50 mg twice daily dose is recommended based upon reaching the IC50 and showing acceptable tolerability. Safety data in AML are based upon three studies: monotherapy in FLT3 mutated patients (2104 Core; N=20), monotherapy in relapsed AML or ineligible for chemotherapy (2104E1; N=95) and front-line combination therapy with daunorubicin and cytarabine (2106; N=69). (Stone 2005, Fischer 2010, Stone 2012). Data from the maintenance phase of the Phase III (2301, CALGB 10603 Ratify) study would also be very informative but the ongoing trial remains blinded at this time. Single agent safety data from 2104E1 will be discussed.

In study 2104E1, patients were randomized to receive midostaurin at doses of 50 mg b.i.d. or 100 mg b.i.d. Of the patients enrolled, 73% were relapsed/refractory and 61% were greater than 60 years of age. Six patients had previously undergone HSCT. Midostaurin was generally well tolerated at both dose levels. All 95 patients experienced at least one AE regardless of relationship to study drug. The most frequent events were grades 1 or 2 nausea (61%; Grade 3 was 1%), vomiting (49%; Grade 3 was 1%), diarrhea (44%; Grade 3 or 4 was 5%), fatigue (38%; Grade 3 was 3%), pyrexia (35%; Grade 3 was 7%) and dyspnea (29%; Grade 3 or 4 9%). The most commonly reported grade 3 / 4 AEs were febrile neutropenia (21%), thrombocytopenia (19%), neutropenia (12%), anemia (13%) and pneumonia (12%). [Inv Brochure ed 16, Table 6-20] The decreases observed in the hematology parameters were as expected for this patient population. Only one patient discontinued treatment due to a hematologic

abnormality (grade 3 febrile neutropenia). The majority of new or worsened biochemistry abnormalities were of CTC grade 1-2. There were grade 3 or 4 abnormalities in AST/ALT in 13% patients (2 were Grade 4, both receiving 100 mg b.i.d.), amylase 7% and albumin 5%. The full table of newly occurring or worsening hematology and chemistry abnormalities is shown in the Investigators Brochure.

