10.5 Other Required Reporting

10.51 Adverse events to be graded at each evaluation and pretreatment symptoms/conditions to be evaluated at baseline per the CTCAE v4.0 grading unless otherwise stated in the table below:

System Organ Class (SOC)	Adverse event/Symptoms	Baseline	Each evaluation
--------------------------	------------------------	----------	-----------------

Investigations	Electrocardiogram QT corrected interval prolonged	X	X
	Blood bilirubin increased	X	X
	Alanine aminotransferase increased	X	X
	Aspartate aminotransferase increased	X	X
	Lipase increased	X	X
Skin and subcutaneous tissue disorders	Rash maculo-papular	X	X

10.52 Submit via appropriate MCCC Case Report Forms (i.e., paper or electronic, as applicable) the following AEs experienced by a patient and not specified in Section 10.51:

10.521 Grade 2 AEs deemed *possibly, probably, or definitely* related to the study treatment or procedure.

10.522 Grade 3 and 4 AEs regardless of attribution to the study treatment or procedure.

10.523 Grade 5 AEs (Deaths)

10.5231 Any death within 30 days of the patient's last study treatment or procedure regardless of attribution to the study treatment or procedure.

10.5232 Any death more than 30 days after the patient's last study treatment or procedure that is felt to be at least possibly treatment related must also be submitted as a Grade 5 AE, with a CTCAE type and attribution assigned.

10.53 Refer to the instructions in the Forms Packet (or electronic data entry screens, as applicable) regarding the submission of late occurring AEs following completion of the Active Monitoring Phase (i.e., compliance with Test Schedule in Section 4.0).

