- 16.325 Adverse Events: All eligible patients that have initiated treatment will be considered evaluable for assessing adverse event rate(s). The maximum grade for each type of adverse event will be recorded for each patient, and frequency tables will be reviewed to determine patterns. Additionally, the relationship of the adverse event(s) to the study treatment will be taken into consideration.

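### Adverse events are tabulated by maximum grade with no comparison to baseline, so cytopenias present at entry from untreated AML may sit in the Grade 3-4 tables unseparated from on-treatment worsening

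*Combined protocol and SAP*

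**What the plan says.** Section 16.325 is the plan's analysis of adverse events. It covers eligible patients who started treatment and states that "The maximum grade for each type of adverse event will be recorded for each patient", with frequency tables then reviewed for patterns. On causality it adds: "Additionally, the relationship of the adverse event(s) to the study treatment will be taken into consideration". It does not mention baseline grade, change from baseline or a treatment-emergent definition.

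Section 10.51 introduces its list as "Adverse events to be graded at each evaluation and pretreatment symptoms/conditions to be evaluated at baseline per the CTCAE v4.0 grading". The list has six terms: QTc prolongation, bilirubin, ALT, AST, lipase and maculo-papular rash. Section 6.8 requires baseline grading by reference to section 10.5, so it adds no terms.

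For events outside that list, section 10.522 sends to the case report form "Grade 3 and 4 AEs regardless of attribution to the study treatment or procedure". It has no exemption for abnormalities already present at entry.

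The laboratory criteria in section 3.15 cover amylase, lipase, bilirubin, alkaline phosphatase, AST, ALT and creatinine. They set no minimum for neutrophils, platelets or hemoglobin.

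**The concern.** Patients enter with untreated AML, a disease that lowers blood counts. The plan's own definition of complete response in section 11.1 requires neutrophils and platelets to reach set levels, so low counts at entry are anticipated. A maximum-grade table cannot tell a patient who entered at Grade 4 thrombocytopenia and stayed there from one who fell to Grade 4 after treatment. With a single arm, no control group shows how much of the rate is disease.

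Safety and toxicity is a secondary goal (section 2.24). Hematologic events do not count toward the suspension rule in section 16.42, and section 10.32 exempts non-hospitalised count decreases up to Grade 4 from expedited reporting. The tables in section 16.325 are thus the only prespecified summary of the combination's hematologic toxicity.

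The background in section 1.2 describes earlier midostaurin laboratory data in terms of abnormalities that newly appeared or got worse. Of one earlier study it says "The decreases observed in the hematology parameters were as expected for this patient population". That was a monotherapy study in mostly relapsed or refractory patients, so it supplies no entry rate here. It does show that counts in this disease are read against the patients' underlying state, and tables from section 16.325 would not be comparable with a new-or-worsened table.

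**Working it through.** The plan states no figure on this point, so there is none to reproduce. The check has two parts.

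**1. Can an entry cytopenia reach the table?**

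- Entry: section 3.15 has no count threshold, so a patient with Grade 3-4 cytopenia can enrol.
- Baseline grade: section 10.51 requires none for any cytopenia.
- Collection: section 10.522 takes Grade 3-4 events regardless of attribution.
- Summary: section 16.325 keeps the worst grade per event type, with no baseline rule.

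Nothing in this chain removes a Grade 3-4 count that was already there. Whether an unchanged entry abnormality is entered as an on-treatment event is not stated, and the forms are not in the documents. The supported conclusion is that it may be counted.

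**2. How large could the effect be? (Assumptions throughout.)**

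Let *b* be the share of patients at Grade 3-4 for a given cytopenia at entry, and *t* the share of the remainder who newly reach Grade 3-4. Assume that entry abnormalities are counted. N = 24 is the evaluable number in section 16.21. The documents give neither *b* nor *t*.

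- Maximum-grade rate = b + (1 - b)t
- New Grade 3-4 over all patients = (1 - b)t
- New Grade 3-4 among those at risk = (1 - b)t / (1 - b) = t
- Maximum-grade rate minus at-risk rate = b + (1 - b)t - t = b(1 - t)

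With t = 0.4:

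| b | Maximum-grade rate (patients of 24) | New, over all 24 | New, among at risk (number at risk) | Difference b(1 - t) |
|---|---|---|---|---|
| 0.2 | 52% (12.5) | 32% (7.7) | 40% (19.2) | 12 points |
| 0.4 | 64% (15.4) | 24% (5.8) | 40% (14.4) | 24 points |
| 0.6 | 76% (18.2) | 16% (3.8) | 40% (9.6) | 36 points |

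Numbers at risk are 24(1 - b). Across b from 0.2 to 0.8 and t from 0.2 to 0.6, the share of patients counted at Grade 3-4 who were already there at entry, b / [b + (1 - b)t], runs from 0.2/0.68 = 29% to 0.8/0.84 = 95%.

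The maximum-grade rate rises with *b* although the new-event rate *t* is fixed. The new-event count over all 24 falls with *b* for the same *t*, because patients who enter at Grade 3-4 cannot contribute. Only the at-risk rate is stable, so the denominator matters as much as the shift table.

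**The case against.** The strongest reply is that the plan does not ignore baseline and loses no count data. The test schedule in section 4.0 has a pre-treatment adverse event assessment and a blood count with differential before treatment and on cycle 1 day 1. Section 18.1 has a baseline adverse event form. Every event is given one of five attributions (section 10.3), including unlikely and unrelated, and section 16.325 says relationship will be considered. No formal decision uses the hematologic tables. All of this stands, and it rules out four stronger readings that a reader might infer:

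- *Symptoms are not graded at baseline.* One is: "Rash maculo-papular" is on the list. Section 10.51 sets a minimum and does not bar recording other conditions. What is missing is a required baseline grade for fatigue, nausea, vomiting and diarrhea.
- *Entry cytopenias are reported as regimen toxicity.* Section 10.522 is a collection rule and assigns no cause. An entry cytopenia can be recorded as unrelated.
- *Toxicity cannot be told apart from entry status.* Baseline cytopenia grades can be derived from the pre-treatment counts. The gap is in the analysis rule.
- *Safety monitoring is compromised.* The suspension rule in section 16.42 counts only non-hematologic events of Grade 4 or higher that are at least possibly related.

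Attribution does not close the gap, however. The plan gives no rule for how it enters the tables. Decitabine's listed toxicities include neutropenia, thrombocytopenia and anemia (section 15.27), so a persisting disease cytopenia could readily be called possibly related. The attribution review in section 16.42 looks only at Grade 4-5 events called unrelated or unlikely, and nothing checks for over-attribution.

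It is also fair to object that counting only grades above baseline brings its own bias, since a patient who enters at Grade 4 has little or no room to be counted. That is right, and it is why an at-risk denominator is needed.

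**Conclusion.** The point holds as a weakness in the analysis rule. The all-attribution Grade 3-4 tables may include cytopenias present at entry, and the plan as written does not separate them from worsening on treatment. The required baseline grading also leaves out fatigue and gastrointestinal symptoms, which, unlike counts, cannot be recovered from laboratory values.

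The excess cannot be sized from the documents. The illustrative differences of 12 to 36 percentage points rest on assumed values of *b* and *t*, and on entry abnormalities being entered as events. They show direction and possible scale and are not estimates. The efficacy decision and the accrual-suspension rule do not change. The consequence is for the interpretation of a secondary safety result, and the remedy is cheap enough that the change should be made.

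**What to change.** In section 16.325:

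1. Derive baseline CTCAE grades for neutrophils, platelets, hemoglobin and white cells from the pre-treatment blood count already required.
2. Add a shift table of worst on-treatment grade by baseline grade.
3. Report new or worsened Grade 3-4 rates among patients below the grade in question at baseline, and state that denominator each time.
4. Keep the maximum-grade table beside it, shown once for all attributions and once for events at least possibly related.

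In section 10.51, add fatigue, nausea, vomiting and diarrhea to the Baseline column.

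The cost is one extra table, a few more baseline form entries, and smaller denominators for the at-risk rates. No new visit, test or patient is needed. One limit remains: in a single arm, worsening from baseline still does not separate drug effect from progressing leukemia, and the report should say so.

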16.33 Correlative Analyses

- 16.331 Prognostic and predictive factors including age and FLT3 mutation by ITD vs. TKD vs. both will be assessed. These factors will be summarized and used to help characterize the types of patients accrued to this trial. In addition, we will explore differences in the distributions of these risk factors by clinical outcome (CR/CRi vs. not, OS and DFS). Nonparametric quantitative comparisons by group will be made as appropriate (Fisher's exact or Wilcoxon rank sum). Kaplan-Meier methods

and log rank statistics will be used to compare between groups for time to- event measures. Given the limited number of patients, the difference in risk factor distribution by outcome will be largely exploratory.

16.332 MRD will be assessed by PCR for FLT3 mutation (if FLT3 is repeated) or flow cytometry . MRD status will be correlated with response using Fisher's exact test. In addition, the relationship between MRD status (positive vs. negative) and disease-free survival will be evaluated using landmark analyses.

16.34 Over Accrual: If more than the target number of patients are accrued, the additional patients will not be used to evaluate the stopping rule or used in any decision making processes; however, they will be included in final endpoint estimates and confidence intervals.

16.4 Data & Safety Monitoring:

16.41 The principle investigator(s) and the study statistician will review the study at least twice a year to identify accrual, adverse event, and any endpoint problems that might be developing. The Mayo Clinic Cancer Center (MCCC) Data Safety Monitoring Board (DSMB) is responsible for reviewing accrual and safety data for this trial at least twice a year, based on reports provided by the MCCC Statistical Office.

16.42 Adverse Event Stopping Rules: The stopping rules specified below are based on the knowledge available at study development. We note that the Adverse Event Stopping Rule may be adjusted in the event of either (1) the study re-opening to accrual or (2) at any time during the conduct of the trial and in consideration of newly acquired information regarding the adverse event profile of the treatment(s) under investigation. The study team may choose to suspend accrual because of unexpected adverse event profiles that have not crossed the specified rule below.

Accrual will be temporarily suspended to this study if at any time we observe events considered at least possibly related to study treatment (i.e. an adverse event with attribute specified as "possible," "probable," or "definite") that satisfy one of the following:

- if 4 or more patients in the first 12 treated patients experience a grade 4 or higher non-hematologic adverse event at least possibly related to treatment excluding infections and hypophosphatemia, hypocalcemia, hypo- or hyperkalemia, hyperuricemia as these abnormal lab results tend to resolve quickly (≤ 7 days) without affecting or jeopardizing patient safety.
- if after the first 12 patients have been treated, 30% of all patients experience a grade 4 or higher non-hematologic adverse event at least possibly related to treatment excluding infections and hypophosphatemia, hypocalcemia, hypo- or hyperkalemia,

hyperuricemia as these abnormal lab results tend to resolve quickly (≤ 7 days) without affecting or jeopardizing patient safety.

We note that we will review grade 4 and 5 adverse events deemed “unrelated” or “unlikely to be related”, to verify their attribution and to monitor the emergence of a previously unrecognized treatment-related adverse event.

16.5 Results Reporting on ClinicalTrials.gov: At study activation, this study will have been registered within the “ClinicalTrials.gov” website. The Primary and Secondary Endpoints along with other required information for this study will be reported on ClinicalTrials.gov. For purposes of timing of the Results Reporting, the initial estimated completion date for the Primary Endpoint of this study is 2.5 years after the study opens to accrual. The definition of “Primary Endpoint Completion Date” (PECD) for this study is at the time the last patient registered has been followed for at least 6 months.

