The FMS-like tyrosine kinase 3 (FLT3) belongs to the group of class III receptor tyrosine kinases. It belongs to a family of important signaling receptors that include c-KIT, c-FMS, and PDGFR. FLT3 is a growth factor receptor involved in hematopoietic cell growth and differentiation. FLT3 receptor and its ligand (FL) also play an important role in survival and self-renewal of early hematopoietic progenitors, monocytic precursors and in lymphoid development. Activation of FLT3 results in receptor auto-phosphorylation leading to downstream signaling of the RAS/MAPK, JAK/STAT5, and PI3K/AKT pathways. In normal bone marrow (BM), FLT3 is expressed on progenitor cells and regulates stem cell proliferation. As hematopoietic progenitor cells differentiate and mature, FLT3 expression is normally lost.

In AML, signaling of FLT3 pathway is often activated and leads to malignant blast cell proliferation, in part due to over expression of FLT3 receptor in leukemia cells. However, a major research advance was the identification of mutations occurring in the FLT3 gene in AML patients. It is the most common somatic mutation identified in AML, with an incidence of about 25% ([Kindler 2010](#), [Kottaridis 2001](#)). Two major types of FLT3 gene mutation have been identified: 1) internal tandem duplication (ITD) and 2) tyrosine kinase domain (TKD) point mutations (PM) and ITDs make up a majority of FLT3 mutations in newly diagnosed patients ([Thiede 2002](#)). These duplications are the result of 3 to > 400 base pairs inserted into the receptor in-frame ([Schnittger 2002](#)). The ITDs promote ligand-independent FLT3 receptor dimerization and signal activation, culminating in cellular proliferation ([Kiyoi 1998](#), [Hayakawa 2000](#)).

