3.0 Patient Eligibility

3.1 Inclusion Criteria

- 3.11 Age \geq 60 years old.
- 3.12 Unfit for chemotherapy based on investigator assessment or patient not willing to receive intensive induction as advised by investigator.
- 3.13 Untreated, histological confirmed acute myeloid leukemia (AML) based on WHO 2008 criteria (See Appendix IV) with either/or both:
 - FLT3 ITD mutation
 - FLT3 TKD mutation
- 3.14 ECOG Performance Status (PS) 0, 1, 2 or 3 (Appendix II).
- 3.15 The following laboratory values obtained \leq 7 days prior to registration.
 - Serum amylase and lipase \leq 1.5 x ULN
 - Total Bilirubin \leq 1.5 x ULN [Does not apply to patients with isolated hyperbilirubinemia (e.g., Gilbert's disease), in that case direct bilirubin should be \leq 2 x ULN]
 - Alkaline phosphatase \leq 3 x ULN
 - SGOT (AST) \leq 2.5 x ULN
 - SGPT (ALT) \leq 2.5 x ULN
 - Creatinine \leq 2 x ULN
- 3.16 Negative pregnancy test done \leq 7 days prior to registration, for women of childbearing potential only.
- 3.17 Provide informed written consent.
- 3.18 Willing to return to consenting Mayo Clinic (Mayo Clinic's campus in Rochester), for follow-up during the Active Monitoring Phase of the study.
- 3.19 Willing to provide bone marrow aspirate and blood samples for correlative research purposes (see Sections 6.2 and 14.1).

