11.0 Treatment Evaluation

11.1 Complete hematologic response (CR)

Less than 5% blasts in a non-hypocellular marrow with a granulocyte count ≥ 1.0 , and a platelets count ≥ 100 with complete resolution of any extramedullary disease and absence of peripheral blood blasts. The patient is in sustained CR if they have previously achieved a CR and continue to meet the CR criteria (at least 28 days).

CR incomplete (CR_i) is called if patient meets all CR criteria except for residual neutropenia (ANC < $1 \times 10^9/L$) or thrombocytopenia (platelets < $100 \times 10^9/L$)

- 11.11 Complete cytogenetic remission (CCyR)
The absence of chromosome abnormalities (if present at diagnosis) on conventional cytogenetic study using G-banding (at least 10 metaphases present).
- 11.12 Complete molecular remission (CMR)
The achievement of negative PCR for FLT3 mutation (if done and if present at diagnosis).
- 11.13 MRD: Minimal Residual Disease
Positive PCR for FLT3 mutation or flow cytometry for FLT3 overexpression from peripheral blood or bone marrow.
- 11.2 Morphologic leukemia-free state (MLFS):
If bone marrow blasts <5%, absence of Auer rods blasts, absence of extramedullary disease without hematological recovery.
- 11.3 Partial response (PR)
The presence of trilineage hematopoiesis in the bone marrow with recovery of ANC and platelet count to above levels, but with 5-25% bone marrow blasts and $\geq 50\%$ decrease in bone marrow blast percentage from baseline.
- 11.4 No response (NR)
Failure to achieve a PR, MLFS, CRi, or CR.
- 11.5 Relapse:
Disease recurrence after achieving CR. Disease recurrence is defined by blast $\geq 5\%$ in the bone marrow, or recurrence of peripheral blood blasts or extramedullary involvement.
- 11.6 Treatment failure:
Resistant disease: Failure to achieve CR/CRi/PR/morphologic leukemia-free state by the end of 8 cycles of induction .

Note: These patients will be recorded as an objective status of NR to document depth of response but will be considered treatment failures at the time of analysis.

Death in aplasia: Death occurring ≥ 7 days following completion of treatment with aplastic/hypoplastic bone marrow (obtained within 7 days of death) with no evidence of persistent leukemia

Death from indeterminate cause: Death occurring during therapy or < 7 days following treatment completion, or ≥ 7 days following completion of treatment with no blast in the blood but no bone marrow examination available

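### The all-patient Fisher test of MRD against response in 16.332 largely re-measures leukemia burden; MRD should be summarised within CR/CRi instead

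*Combined protocol and SAP*

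**What the plan says.** Section 3.13 admits only patients with a FLT3 ITD mutation, a TKD mutation or both. Section 11.13 defines MRD as "Positive PCR for FLT3 mutation or flow cytometry for FLT3 overexpression from peripheral blood or bone marrow". Section 11.12 separately defines complete molecular remission as "The achievement of negative PCR for FLT3 mutation (if done and if present at diagnosis"). CR in 11.1 rests on morphology and counts, beginning "Less than 5% blasts in a non-hypocellular marrow with a granulocyte count", and uses no FLT3 criterion.

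Section 16.332 plans the analysis: "MRD will be assessed by PCR for FLT3 mutation (if FLT3 is repeated) or flow cytometry", after which "MRD status will be correlated with response using" Fisher's exact test. It states no response grouping, sampling time, significance level or restriction to responders. The same paragraph adds landmark analyses of MRD status against disease-free survival, without a landmark time or analysis set. The remark that comparisons are largely exploratory belongs to the risk-factor analyses in 16.331 and is not repeated in 16.332.

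**The concern.** MRD is useful when it separates patients whom morphology treats alike, that is, patients already in remission. Run over all patients, the planned test mainly sets patients with visible leukemia against patients without it. Since the marker is the mutation that qualified everyone for entry, a patient whose leukemia persists would ordinarily still carry it. Non-response and MRD positivity then become two readings of the same disease burden.

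Reading MRD as measured in responders only does not rescue the test. No responder versus non-responder contrast would be left, only a comparison of grades of response, and no such grouping is given.

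What is at stake is interpretation. A small p-value could be taken as evidence that MRD is informative in this setting when it mostly restates that non-responders have leukemia.

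**Working it through.** **Plan's own figures.** The plan states no figure for this test. The design figures, used here only to choose realistic numbers of responders, reproduce. With 24 evaluable patients and success at 5 or more CR/CRi, the exact binomial tail is 0.0851 at a true rate of 10% (stated 0.09) and 0.8889 at 30% (stated 0.89). Five responders is the success threshold in 16.211, and 0.30 × 24 = 7.2, so about seven is the target.

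**Assumptions not in the documents.** All 24 patients have an MRD result, every non-responder is MRD-positive, and the test is two-sided at 0.05.

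**Formula.** With r responders, k of them MRD-negative, and no MRD-negative non-responders, the two-sided Fisher p-value in the cases below equals C(r,k) / C(24,k), because no table in the opposite direction is as improbable as the one observed. C(24,2) = 276 and C(24,3) = 2024.

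| Responders | MRD-negative | Calculation | p |
|---|---|---|---|
| 5 | 2 | 10/276 | 0.036 |
| 6 | 2 | 15/276 | 0.054 |
| 6 | 3 | 20/2024 | 0.010 |
| 7 | 2 | 21/276 | 0.076 |
| 7 | 3 | 35/2024 | 0.017 |
| 8 | 3 | 56/2024 | 0.028 |

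With 5, 7 or 8 responders, p falls below 0.05 while most responders are still MRD-positive. With 6 responders, half must be negative.

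**How often this would happen.** Let q be the MRD-negative rate among responders (assumed). With 7 responders the test needs at least 3 negatives, so the chance of p ≤ 0.05 is P(X ≥ 3) for X ~ Binomial(7, q). The last column lets the number of responders vary at a 30% response rate.

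| q | 7 responders | Number of responders random |
|---|---|---|
| 0.2 | 0.15 | 0.17 |
| 0.3 | 0.35 | 0.38 |
| 0.5 | 0.77 | 0.78 |
| 0.7 | 0.97 | 0.96 |

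If 10% of non-responders are MRD-negative instead of none, and the number of responders is random, the chance runs from about 0.05 at q = 0.2 to 0.97 at q = 0.9.

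**Incomplete testing.** Suppose 12 patients are tested and 6 of them are responders. Four negatives give 2 × C(6,4)/C(12,4) = 30/495 = 0.061. Five give 2 × C(6,5)/C(12,5) = 12/792 = 0.015. So 5 of 6 would have to be negative.

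**Definitions side by side.** A patient who is PCR-negative but FLT3-overexpressing by flow is in complete molecular remission under 11.12 and MRD-positive under 11.13. Section 16.332 gives no rule for such discordance.

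**The case against.** A reader might infer that the association is true by definition. The documents do not support that. CR/CRi uses no FLT3 status, so a responder can be MRD-positive. Nor do they say that every non-responder keeps a detectable clone. If response means CR/CRi, the grouping in 16.331, then patients in morphologic leukemia-free state count as non-responders and may be MRD-negative. Death in aplasia (11.6) is a treatment failure without evidence of persistent leukemia. Section 11.13 also accepts peripheral blood, which could be negative while marrow blasts remain.

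A reader might also infer that the test is bound to be significant. At q of 0.2 to 0.3 it would miss 0.05 more often than reach it, and conditional repeat testing works against it. Sampling time matters too. The only post-baseline FLT3 PCR in the test schedule is at early discontinuation or end of treatment, when a relapsed responder could be positive and weaken the association. Section 14.21 does plan FLT3 sequencing for MRD on the correlative samples.

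Nor is the prognostic question left out, because the disease-free survival landmark analysis relates MRD to later outcome. But it is not stated to be confined to CR/CRi, and section 16.3 defines progression-free survival, not disease-free survival.

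Finally, section 1.1 says that in normal marrow "FLT3 is expressed on progenitor cells and regulates stem cell proliferation", from which a reader might conclude that normal marrow would count as MRD-positive. Section 11.13 requires overexpression, which 1.1 associates with leukemia cells, so that does not follow. The conflict between 11.12 and 11.13 is real but secondary: complete molecular remission enters no analysis in section 16.

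These points limit the strength of the claim. They do not make the all-patient test informative about what MRD adds to morphology.

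**Conclusion.** The point stands in a limited form. The all-patient Fisher test is largely built in, given the expectation that most patients with persistent leukemia remain FLT3-positive. Whether or not it reaches significance, it does not show whether MRD adds to morphology. It can reach p < 0.05 on as few as 2 MRD-negative patients of 5 responders or 3 of 7, but not on 2 of 7. These figures rest on complete testing of 24 patients, no MRD-negative non-responders and an assumed two-sided 0.05 level. The analysis is correlative and does not touch the primary decision rule, so this is a cheap improvement and not a flaw in the trial's main conclusion.

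**What to change.** In 16.332:

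- Make the main MRD-response summary the MRD-negative proportion among CR/CRi patients, with an exact confidence interval and the number tested.
- Restrict the disease-free survival landmark analysis explicitly to CR/CRi patients.
- Keep any cross-tabulation of MRD by response over all patients as descriptive only.
- Report FLT3-mutation results (PCR or sequencing) and flow results separately, with matching wording in 11.13, so that 11.12 and 11.13 cannot classify one patient in opposite ways.

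The cost is a wording change, with no new samples or patients. The downside is a smaller analysis set and a wide interval: 3 MRD-negative of 7 gives an exact 95% interval of about 10% to 82%. That width shows how little the trial can say about MRD among its responders.
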